4. **Urine Samples to quantitate Excretion of Lactulose and ¹³C-Mannitol after Oral Ingestion** of lactulose and ¹³C mannitol (5:1 ratio by mass) (47). The 0-2h urine most closely reflects small intestinal permeability and 8-24h urine reflects colonic permeability (46). HPLC-tandem mass spectrometry will be used for detection of the sugars (Mayo Clinic CTSA Lab). Baseline and post treatment small bowel and colonic permeability will be performed for every patient.

*Cumulative (Cum) excretion (0-2h and 8-24h) = Concentration of sugar (µg/mL)] * total urine volume (mL).*

Lactulose: mannitol ratio (L:M R) is: 0.2 x (Cum excretion lactulose) / (Cum excretion ¹³C-mannitol).

5. **Sigmoidoscopy and Mucosal Biopsies from sigmoid will now be optional.** Participants will have the option to complete sigmoidoscopy at the beginning, end, both time points or refrain from completing this portion of the study. If participants agree to perform the sigmoidoscopy, it will be performed in all fasting participants in the Clinical Research unit, and in the same time of day (7-8am), with the patients' medications stopped 48 hours before the biopsies for the baseline studies. The biopsies will be collected in formalin or RNAlater solution (Ambion, Austin, TX) and stored at -80°C until further analyzed.

RESEARCH PLAN for Randomized controlled trial of colessevelam in IBS-D with high fecal BA.

Hypotheses: BA sequestration normalizes colonic *functions* in IBS-D with increased fecal BA excretion.

Specific Aim: To compare with a randomized trial (*n=15 per treatment group*), *effects of colessevelam 1.875g bid and placebo treatment, on colonic transit, bowel functions, permeability and tight junction expression in rectosigmoid mucosa* of IBS-D with fecal BA>2000 µmoles/48h (upper limit of normal).

Rationale: BA diarrhea is increasingly recognized as a subtype of IBS-D (39,41). In an open-label study (27), we identified beneficial effects of colessevelam in the treatment of IBS symptoms in patients with high total fecal BA excretion (>2000µmoles/48h), elevated primary bile acids (>4%) with elevated total fecal bile acids (>1,000 µmol/48h), or primary bile acids > 10%, elevated C4 (> 40 ng/mL), and decreased FGF19 (<80 pg/mL) (section C.1.g and figure 7)).

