Human subjects and design: 30 IBS-D patients with BAM will be randomized (15/group) in 4-week double-blind, parallel-group trial to Colesevelam, 1.875g b.i.d. or placebo. Patients will be stratified on gender and BMI; we anticipate 90% female and 75% BMI >30kg/m².

[figure not shown]
Experimental procedures: Effects of colesevelam/placebo on symptoms (daily stool diaries), as well as colonic transit, fecal bile acid and fat excretion and fasting serum C4 and FGF-19, intestinal permeability and TJ expression in rectosigmoid mucosal biopsies at baseline and at end of 28 days' treatment.

Primary endpoints: 1. Bowel movements/week; 2. Stool consistency based on Bristol Stool Form Scale, BSFS.

Secondary endpoints: 1. Quantitative total fecal BAs; 2. Proportion of secretory BA (CDCA, DCA) in stool; 3.

Fasting serum C4 and FGF-19 levels; 4. Colonic transit, geometric center at 24 and 48 hours; 5. Intestinal and colonic permeability (mannitol, lactulose excretion); 6. TJ expression in rectosigmoid mucosa.

Colesevelam Study Design

This study consists of ten visits to Mayo Clinic at the Charlton 7 Clinical Research Trials Unit (CRTU). Some of the visits can be combined.

Visit 1 (Screen visit) Volunteers will be asked to come to the Charlton 7 to review and sign this informed consent form and all have all their questions answered. This visit will require about 90 minutes.

- **QUESTIONNAIRES:** Volunteers will be asked to complete two questionnaires.
 1. Bowel Disease Questionnaire, which asks questions about their bowel symptoms
 2. Hospital Anxiety and Depression Inventory, which asks about any anxiety or depression they are currently feeling
 3. Quality of Life Questionnaire, which ask you how your bowel symptoms are affecting your life
 4. Symptom Checklist, which ask you about any symptoms you are currently feeling
- **VITAL SIGNS, HEIGHT AND WEIGHT:** A nurse will take your height, weight and vital signs (pulse, blood pressure, respiration rate and temperature).
- **HISTORY AND BRIEF PHYSICAL EXAM:** A study physician will review their medical history, current medications and supplements and perform a physical exam.
- **POSSIBLE BLOOD DRAW:** A small amount of blood may be taken if the study physician determines that blood tests need to be run to see if they qualify for the study. Such as serum alphaC4 or FGF19.

If the study physician finds the volunteer eligible for the study, they will be asked to participate in the rest of the study.

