- **ENEMA**: Participants will need to prepare the colon for the sigmoidoscopy by means of a tap water enema at the CRTU. A CRTU nurse will give a tap water enema. Two enemas may be given if needed.
- **FLEXIBLE SIGMOIDOSCOPY WITH BIOPSIES**: A sigmoidoscopy is a lower endoscopy that uses a flexible endoscope to visually inspect the lining of the sigmoid colon. Several biopsies of the lining of the colon will be removed for examination under a microscope, TJ protein expression, proteomics and RNA sequencing.. No sedation is needed. The nurse will review information regarding post-endoscopy care and the participant will be dismissed.

Visit 5 (Study Medication pickup) Participants will be asked to report to the desk on Charlton 7 (no fasting required).The visit should take approximately 15-30 minutes.

- **PREGNACY TEST**, if needed: A urine sample will be collected for a pregnancy test from women who can get pregnant if it was not done within 48 hours of this study day. The results of this test must be negative in order to continue the study.
- **STUDY MEDICATION**: The nurse will dispense a 5 week supply of the Colesevelam/placebo and instruct participants to take 3 tablets orally twice daily with lunch and supper.
- **SINGLE RANDOMSTOOL SPECIMENS**: Returned as instructed
- **DIARIES RETURN**: Participants will be asked to return the completed 7-day Pretreatment Bowel diary
-

TREATMENT: Participants will take 1875 mg (3 tablets [625 mg/tablet]) of the medication orally twice daily with lunch and supper for 4-5 weeks. They also will be asked to complete the following visits after 21 days of treatment with the treatment fat diet and stool collections completed after the transit/permeability and flex sig/biopsy tests. A separate stool sample collection kit will be provided on Visit 6 to be returned before the flexible sigmoidoscopy. No special diet is required with this particular stool collection.

Note: Treatment Bowel diary will not be completed by participants during high fat diet.

Visit 6 (Treatment testing) Participants will be asked to report to the desk on Charlton 7 after an 8 hour fast (no food/drink, a small amount of water is OK). And the avoidance of artificial sweeteners 48 hours before and during the permeability testing (Visits 6-7). This visit will require about 9-10 hours total.

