The risks to the participants are reasonable since many procedures are noninvasive (other than sigmoidoscopy with biopsies), the research team has vast experience in the proposed testing, there is no risk of any significant morbidity or mortality, and precautions are taken to minimize discomfort or adverse effects. Radiation exposure is being kept to the minimum that allows successful completion and data acquisition. There is a high likelihood (e.g., investigator’s record and expertise, validated methods, statistical power) of obtaining meaningful, useful information in each specific aim.

5. Data and Safety Monitoring Plan (DSMP)

Name of Principal Investigator (PI) – [name].

Study Overview

Brief Description of the Purpose of the Study - This study assesses the effect of bile acid sequestration in patients with IBS-D and bile acid malabsorption in a randomized controlled trial and a study of the patient’s DNA and the transcriptome and proteome of the mucosa of the rectosigmoid colon.

This study does not involve administration of any investigational agent and therefore poses minimal risk to participants. Because of this low risk status, the Data Safety Monitoring Plan (DSMP) for this study focuses on close monitoring by the PI in conjunction with an Independent Monitor. Adverse events will be reported to the NIH and to the Mayo Clinic IRB.

Adherence Statement – The Data Safety Monitoring Plan (DSMP) outlined below will adhere to the protocol approved by the Mayo Clinic IRB.

III. Confidentiality

A. Protection of Subject Privacy – During this study, medical history and physical examination will be performed, and questionnaires will be administered. Additional research material will be: review of medical records (of those who authorize review of the records for research purposes), quantitation of gastrointestinal and colonic transit with an external gamma camera, venous blood samples from which DNA will be extracted and stored, venous blood samples for measurement of factors reflecting BA metabolism, urine and stool

collections, colonic mucosal biopsy collections and expression of mRNA and proteins in biopsies, and measurements of rectal motility.

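### Tight-junction expression remains a secondary endpoint at baseline and day 28, but biopsies are now optional, so 15 per group is not assured for it and the stated ANCOVA has no place for baseline biopsies.

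*Combined protocol and SAP*

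**What the plan says.** Biological Samples Collected, item 5, states the current rule: "Participants will have the option to complete sigmoidoscopy at the beginning, end, both time points or refrain from completing this portion of the study". Visits 4 and 9 in the Colesevelam Study Design are both marked optional.

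Other current sections read as if biopsies were universal:

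- The Specific Aim, at the front and again in the Research Plan, attaches "n=15 per treatment group" to a trial whose outcomes include "permeability and tight junction expression in rectosigmoid mucosa".
- Human subjects and design: "30 IBS-D patients with BAM will be randomized (15/group) in 4-week double-blind, parallel-group trial".
- Experimental procedures: "TJ expression in rectosigmoid mucosal biopsies at baseline and at end of 28 days' treatment". TJ expression is secondary endpoint 6.
- Studies on Sigmoid Mucosal Biopsies still describes samples taken from every patient.

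The Statistical analyses paragraph gives one method, an intention-to-treat ANCOVA with BMI, gender, baseline colonic transit and baseline fecal bile acid (BA) excretion as covariates. It does not list baseline TJ expression, does not say whether the response is the end value or the change, and has no rule for missing biopsies. Table 3 has no TJ row.

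The Treatment paragraph says the kit for a separate on-treatment stool sample is "to be returned before the flexible sigmoidoscopy".

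**The concern.** A participant can contribute a baseline biopsy, an end biopsy, both or neither. The plan does not say who enters the TJ comparison, what the response is, or how incomplete pairs are handled.

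Two things are at stake. First, a null TJ result could be read as coming from 15 per group when the number biopsied may be much smaller. Secondly, under the stated covariate list the baseline biopsies do no work if the response is the end value. If the response is change, anyone without a baseline biopsy is lost. In a trial this small, either choice gives up precision that a standard model would recover at no extra burden to participants.

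A smaller consequence concerns the on-treatment stool sample, whose return is timed only by a procedure that some participants will decline.

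**Working it through.** **1. The plan's own power figure.** Inputs from Table 3: stool frequency SD 6.6 and detectable difference 7.00; stool form SD 1.0 and difference 1.06. A two-sample t-test with 15 per group and two-sided α = 0.05 gives:

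- frequency: d = 7.00/6.6 = 1.061, power 80.1%
- form: d = 1.06/1.0 = 1.06, power 80.0%

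The stated figure of about 80% reproduces. It is stated for stool frequency and form only and is unaffected by the biopsy rule.

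**2. What 15 per group, or fewer, would mean for TJ expression.** The plan gives no TJ effect size. For illustration I take the gap between healthy and IBS-D means in Table 2 as complete normalisation, with the IBS-D SD.

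- ZO-1: (1.00 − 0.960)/0.046 = 0.040/0.046 = 0.87
- Occludin: (1.00 − 0.931)/0.025 = 0.069/0.025 = 2.76

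The numbers below 15 are assumptions, because the documents give no expected uptake.

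| End biopsies per group | ZO-1 power |
|---|---|
| 15 | 63% |
| 10 | 45% |
| 8 | 37% |
| 5 | 23% |

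ZO-1 would need about 22 per group for 80%. Occludin still has about 97% at 5 per group.

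**3. What each analysis can use.** Assume 6 paired and 3 end-only participants per arm, equal SD at both times, and baseline-to-end correlation r. Variances of the arm difference, in SD² and with variances treated as known, are:

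- End value, no baseline TJ (the listed covariates are ignored here): 2/(6 + 3) = 0.222.
- Change from baseline, paired only: 2 × 2(1 − r)/6.
- ANCOVA with baseline TJ added, paired only: 2(1 − r²)/6.
- Constrained longitudinal model (common baseline mean): 2/[6/(1 − r²) + 3].

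| r | End value | Change, paired | ANCOVA + baseline TJ, paired | Constrained model |
|---|---|---|---|---|
| 0.3 | 0.222 | 0.467 | 0.303 | 0.208 |
| 0.5 | 0.222 | 0.333 | 0.250 | 0.182 |
| 0.7 | 0.222 | 0.200 | 0.170 | 0.135 |

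Against the end-value analysis, the constrained model cuts the standard error by about 3%, 10% and 22%. It has the smallest variance in every row. Simply adding baseline TJ to the ANCOVA does worse than the end-value analysis at r = 0.3 and 0.5, because it discards end-only participants.

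**4. Start-only biopsies.** A generalised least squares check at r = 0.5 gives 0.1818 with 0, 3 or 9 start-only participants per arm. With balanced arms they add nothing to the treatment contrast. The gain comes from combining paired baselines with end-only biopsies.

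**5. Stool return.** At baseline, Visit 5 lists the random stool specimen, and every participant attends that visit. For the separate on-treatment sample, the text before Visit 6 and the Visit 6 list both refer only to the sigmoidoscopy. Visit 10 lists diaries and unused medication but no stool.

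**The case against.** The best defence is that 15 per group is the randomised size, correctly stated, and was never a promised biopsy count. That stands. Full uptake remains possible, so a reader who infers that the plan fails to deliver 15 per group goes beyond the documents.

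A reader might also infer that the plan claims power for TJ expression, because the section on the importance of the knowledge cites statistical power among the reasons for a high likelihood "of obtaining meaningful, useful information in each specific aim". That is general benefit-risk wording. The Statistical power paragraph confines its claim to stool frequency and form. The ZO-1 shortfall also exists at the full 15 per group, so optional biopsies worsen it but do not create it. It depends on the SD chosen: pooling the two Table 2 SDs, weighted by their degrees of freedom, gives d = 1.02 and 77% at 15. Table 2 also describes IBS-D in general, not patients selected for bile acid malabsorption.

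The laboratory section says TJ mRNA will be compared statistically and cites two prior studies, so the ANCOVA may not be the only method intended. That text names no model, response or analysis set and does not fill the gap.

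Finally, the gain from the mixed model rests on an assumed split and correlation, and at r = 0.3 it is slight. That is fair, but the model costs nothing and also settles how incomplete pairs are handled.

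**Conclusion.** The point holds as an unreconciled passage and a missing analysis rule for one secondary endpoint. Fifteen per group is not assured for TJ expression, no power is stated for it, and the stated ANCOVA makes poor use of partly paired data. A prespecified constrained model would reduce the standard error by about 3% to 22% for correlations of 0.3 to 0.7, given the assumed 6 paired and 3 end-only per arm.

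Two stronger readings are not supported. Start-only biopsies are not wasted information, since with balanced arms they carry none about the treatment contrast. Nor do the documents support material bias from choosing the end biopsy after treatment: they do not say when that choice is made, and the trial is double-blind. It remains true that the comparison covers those who volunteer for biopsy, not all randomised participants. The primary endpoints and their power are untouched.

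**What to change.** 1. Prespecify, before unblinding, a linear mixed model for TJ expression with a common baseline mean across arms and small-sample degrees of freedom, using every available biopsy.
2. Keep 15 per group as the randomised size. State that TJ results apply to participants who provide biopsies, report the number per arm at each time point, and label the endpoint exploratory. Bring the Specific Aim, the Experimental procedures and the biopsy methods text into line with item 5.
3. Tie return of the on-treatment stool sample to a visit that every participant attends.

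The cost is wording and a standard model, with no added procedure. The real downside is that TJ expression is formally downgraded from a secondary endpoint.

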- **STOOL COLLECTION:** You will be given a stool kit and will be asked to return a stool sample before your Flexible Sigmoidoscopy.
- If the patient has not had previous qualifying FGF19, C4, primary to total fecal bile acids in the past, then fasting serum blood work for FGF19 and C4 will be completed at the Screen visit. A 48 hour stool

test to evaluate for primary and total fecal bile acids will be conducted first. The remaining study examinations, abbreviated colonic transit test, permeability test, random stool sample, flexible sigmoidoscopy, and gallbladder ultrasound will be postponed by at least one week.

Visit 2 (Pretreatment testing) Participants will be asked to report to the desk on Charlton 7 after an 8 hour fast (no food/drink, a small amount of water is OK), and the avoidance of artificial sweeteners 48 hours before and during the permeability testing (Visits 2-3). The visit should take approximately 45-60 minutes.

- **PREGNACY TEST**, if needed: A urine sample will be collected for a pregnancy test from women who can get pregnant if it was not done within 48 hours of this study day. The results of this test must be negative in order for participants to continue the study.
- **FASTING BLOOD DRAW**: Participants will be asked to give a small amount of blood for DNA, serum alpha C4 and FGF19 testing if not done previously.

DIARY RETURN: Participants will be asked to return the completed 7-day Pretreatment Diary.

- **ABBREVIATED COLONIC TRANSIT TEST/Permeability test**: Participants will be asked to swallow a small capsule containing a small amount of a radioactive substance with a liquid containing a small amount of naturally occurring sugars: lactulose and mannitol. The sugars allow the measurement of the permeability of the small intestine and colon. The participants will be instructed to have breakfast one hour later.

VISITS 3-5 MAY BE COMBINED

Visit 3 (24 hour image) Participants will be asked to report to the desk on Charlton 7 (fasting required) approximately 24 hours after they ingested the capsule containing radioisotope during Visit 2. Ultrasound measurement can be performed before or after the 24 hour image is obtained. The ultrasound gallbladder measurement should take ~ 10-15 minutes. This visit should take approximately 25 minutes.

Visit 4 (Flexible sigmoidoscopy) [OPTIONAL] Participants will be asked to report to the desk on Charlton 7 (no fasting required). The visit should take approximately 75 minutes.

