Visit 7 (24 hour image) Participants will be asked to report to the desk on Charlton 7 (fasting required) for the 24 hour image. Ultrasound measurement can be performed before or after the 24 hour image is obtained. The ultrasound gallbladder measurement should take ~ 10-15 minutes. The visit should take approximately 25 minutes.

VISITS 8 AND 9 MAY BE COMBINED

Visit 8 (48 hour image and urine collection return) Participants will be asked to report to the desk on Charlton 7 (no fasting required) to drop off their 8-24 hour urine collection and have the 48 hour image taken. The visit should take approximately 10 minutes.

Visit 9 (Flexible sigmoidoscopy) [OPTIONAL] Participants will be asked to report to the desk on Charlton 7 (no fasting required). The visit should take approximately 75 minutes.

- **ENEMA**: same as Visit 4
- **FLEXIBLE SIGMOIDOSCOPY WITH BIOPSIES**: same as Visit 4

Visit 10: End of Study:

- **DIARIES RETURN**: Participants will be asked to return the completed Treatment Bowel diary
- **MEDICATION RETURN**: On the last visit participants will be asked to return any unused medication.

Statistical analyses: Effects of treatment will be compared (using Intention-To-Treat principles) using ANCOVA with BMI, gender, baseline colonic transit and baseline fecal BA excretion as covariates.

November 1 2018: at least 75% of the participants will have completed all study procedures. We plan to complete an interim analysis in order to submit an abstract for a national gastroenterology meeting in May 2019. We anticipate completing all studies in all participants by the time the data need to be presented. At that time, we shall present the data from the ENTIRE patient cohort; that analysis will be used for the one full manuscript emanating from these data.

A senior statistician will review the interim analysis results and analyze the data related to the previously determined primary endpoints. All members of the study team and the investigative team will remain blinded to treatment arm assignment and treatment arm results until the completion of the study. Thus, this would not affect the p value when the study is completed.

Statistical power: Based on our previous open-label study, the proposed sample size (15 per group) has

Response	Mean (SD)	Detectable Δ
#Stools /week	15.1 (6.6)	7.00
Stool Form (BSFS 1-7 scale)	4.4 (1.0)	1.06
Total Fecal BA excretion μ moles/48h	3496 (2456)	2650
Fecal Fat g/24h	6.8 (3.1)	3.30
Serum C4 ng/mL	72.3 (4.3)	45

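### The sampling section requires fasting biopsies at 7-8 am, but both biopsy visits waive fasting, so a participant may be biopsied fasted at baseline and fed at the end of treatment

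*Combined protocol and SAP*

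**What the plan says.** Biological Samples Collected, item 5, makes sigmoidoscopy optional at either, both or neither of the two time points. For those who agree, it sets a sampling condition: "it will be performed in all fasting participants in the Clinical Research unit, and in the same time of day (7-8am").

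The visit descriptions under Colesevelam Study Design read differently:

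- Baseline: "Visit 4 (Flexible sigmoidoscopy) [OPTIONAL] Participants will be asked to report to the desk on Charlton 7 (no fasting required").
- End of treatment: "Visit 9 (Flexible sigmoidoscopy) [OPTIONAL] Participants will be asked to report to the desk on Charlton 7 (no fasting required").
- Neither description gives a time of day.

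Two combining rules apply. At baseline, "VISITS 3-5 MAY BE COMBINED", and the first visit of that group is a fasting one: "Visit 3 (24 hour image) Participants will be asked to report to the desk on Charlton 7 (fasting required"). At the end of treatment, "VISITS 8 AND 9 MAY BE COMBINED", and the partner visit is not a fasting one: "Visit 8 (48 hour image and urine collection return) Participants will be asked to report to the desk on Charlton 7 (no fasting required").

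Tight-junction expression is listed sixth among the secondary endpoints. The Visit 4 text says the same biopsies also serve proteomics and RNA sequencing. The Statistical analyses paragraph compares treatments by ANCOVA. Its covariates are BMI, gender and the baseline values of colonic transit and fecal bile acid excretion.

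**The concern.** Item 5 shows that the sponsor chose to standardise the tissue samples on fasting state and hour. The visit text drops that standardisation at both biopsies, and the combining rules do not treat the two time points alike. If fed state or time of day affects mucosal expression, two things follow. Variation unrelated to treatment enters the tissue endpoints, and any change from baseline read within one arm may partly reflect a move from fasted to fed sampling. The documents do not provide for recording the last meal or the biopsy time, and neither is a covariate. Such variation could therefore be neither detected nor adjusted for afterwards.

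**Working it through.** **Step 1. The conditions side by side.**

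| | Baseline biopsy | End-of-treatment biopsy |
|---|---|---|
| Biological Samples Collected, item 5 | fasting, 7-8 am | fasting, 7-8 am |
| Visit text, biopsy alone | fasting not required, no time | fasting not required, no time |
| Visit text, combined as permitted | joins Visit 3, fasting required | joins Visit 8, fasting not required |

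The first two rows conflict on fasting at both visits. The third row shows the asymmetry by time point. Visit 7, the fasting counterpart of Visit 3, is outside the end-of-treatment combining rule. Item 5 does not read as a leftover: it already describes the biopsies as optional, as the headings of Visits 4 and 9 do, and the texts still disagree.

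**Step 2. What a fasted-to-fed shift could do.** The plan states no figure on this point, so there is nothing to reproduce. From the documents: two arms, 15 per group, one visit schedule, double-blind. Assumed, because the documents are silent:

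- a fed-state effect s of 0 to 1 SD;
- fed shares at baseline and end (pb, pe) of 0/1, 0/0.5 and 0.25/0.75, the same in both arms;
- a baseline-to-end correlation of 0.5;
- every participant biopsied twice;
- no true drug effect.

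Formulas, in units of the SD at one time point:

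- Within-arm shift = s × (pe − pb).
- Variance of change without a fed-state effect = 2 × (1 − 0.5) = 1.
- SD of change relative to that = √(1 + s² × [pb(1 − pb) + pe(1 − pe)]).
- Between-arm bias = s × (difference between arms in fed share), which is 0 when the shares are equal.

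The within-arm, between-arm and type I error columns come from simulation (40,000 replicates, t test on change from baseline). The last column is from the formula.

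| Fed share, baseline/end | s | Within-arm shift | Between-arm difference | Type I error | SD ratio |
|---|---|---|---|---|---|
| 0 / 1 | 0.25 | 0.250 | 0.0007 | 0.0511 | 1.000 |
| 0 / 1 | 0.5 | 0.501 | 0.0018 | 0.0498 | 1.000 |
| 0 / 1 | 1 | 1.002 | 0.0007 | 0.0484 | 1.000 |
| 0 / 0.5 | 0.25 | 0.125 | 0.0000 | 0.0512 | 1.008 |
| 0 / 0.5 | 0.5 | 0.251 | 0.0014 | 0.0504 | 1.031 |
| 0 / 0.5 | 1 | 0.500 | −0.0003 | 0.0508 | 1.118 |
| 0.25 / 0.75 | 0.25 | 0.128 | 0.0022 | 0.0493 | 1.012 |
| 0.25 / 0.75 | 0.5 | 0.251 | 0.0032 | 0.0489 | 1.046 |
| 0.25 / 0.75 | 1 | 0.501 | 0.0024 | 0.0475 | 1.173 |

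For the last row, √(1 + 1 × [0.1875 + 0.1875]) = √1.375 = 1.173. The largest between-arm difference in any run was 0.0044, and it came from a run with s = 0, so it is simulation noise.

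**Step 3. Chance imbalance.** The documents give no biopsy uptake, so these are illustrations only, with each biopsied participant fed with probability one half, independently.

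- With 5 biopsied per arm, the fed counts differ by 2 or more (40 points) with probability 352/1024 = 34%.
- With 8 per arm, they differ by 3 or more (37.5 points) with probability 13,770/65,536 = 21%.

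For scale, a 30-point difference with s = 0.5 would move the between-arm difference by 0.5 × 0.3 = 0.15 SD.

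**The case against.** The strongest reply is that the planned analysis is a comparison of randomised arms. Both arms share one schedule under blinding, so a shift common to both cancels, and the placebo arm exists to absorb it. This stands, and Step 2 bears it out. A reader might infer that the combining rules confound the tight-junction and RNA comparison. The documents do not support that: the asymmetry is by time point, and nothing makes fed shares differ by arm. Nor is a within-arm change the planned comparison, so its possible distortion is a caution for secondary reading.

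A reader might also infer that baseline biopsies will be mostly fasted, or that imbalance between arms is likely. Combining is only permitted, and no share of combined visits and no biopsy uptake is given. If item 5 is followed, both biopsies are fasted.

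It can further be said that waiving a fast does not forbid one, so a site that keeps to item 5 breaches neither text. That is true, but a participant told that fasting is unnecessary has no reason to fast, and no passage says which text prevails.

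The time-of-day half is weaker than the fasting half. Silence at Visits 4 and 9 does not contradict 7-8 am. Combined visits also fall roughly in the morning, because the 24- and 48-hour images follow a capsule taken before breakfast. That does not secure the stated hour, and it does not cover uncombined biopsy visits.

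Finally, Table 2 invites large variance estimates, because its SDs are small (0.046 for ZO-1 and 0.025 for occludin). An assumed shift of 0.05 would double the occludin variance (0.05²/4 = 0.025² for a 50:50 mix). But 0.05 is 2 SD of occludin, and no passage supports a fed-state effect of any size, so that figure only restates its assumption.

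**Conclusion.** The contradiction on fasting is real and affects both biopsy visits. The combining rules allow a participant to be fasted at baseline and fed at the end under the visit text. In expectation the randomised comparison is unbiased. The possible costs are:

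- **Precision:** the SD of change rises by 0% to 17%, for assumed fed-state effects of 0 to 1 SD and the fed shares shown.
- **Within-arm change:** a shift of 0.125 to 1.00 SD, for assumed effects of 0.25 to 1 SD.
- **Chance imbalance between arms:** possible if few participants choose biopsy.

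Every size here rests on those assumptions; the documents give neither the fed-state effect nor the uptake. The point concerns the sixth secondary endpoint, RNA-Seq and proteomics, all from optional biopsies. Stool frequency and stool form, the primary endpoints, are untouched. Severity: minor, but two instructions in force conflict and aligning them is cheap.

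**What to change.** Reconcile item 5 of Biological Samples Collected with the descriptions of Visits 4 and 9. One fasting and time-of-day sampling condition should apply at both biopsies. State how it holds when Visit 4 is combined with Visit 3 and when Visit 9 is combined with Visit 8. Record the time of the last meal and the time of biopsy at each visit, so that departures can be described and, if needed, examined in a sensitivity analysis.

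The cost is a few lines in the visit descriptions and participant instructions, and two recorded times per biopsy. If the item 5 condition is the one kept, participants who choose biopsy must fast beforehand, including at the end of treatment when Visit 8 alone would not require it.
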